#### 5.4.1 Definition of Dose Limiting Toxicities

The DLT period is through completion of induction durvalumab, chemoradiation, and 2 cycles of consolidation durvalumab. NCI Common Terminology Criteria for Adverse Events (CTCAE) v5 will be used in grading adverse events. A DLT will be defined as:

- Any grade of febrile neutropenia regardless of duration or reversibility  Any Grade 4 immune-mediated adverse event (imAE)  Any grade of immune-mediated neurotoxicity.
- Grade  $\geq$  3 colitis
- Grade 3 non-infectious pneumonitis irrespective of duration
- Grade 2 pneumonitis that does not resolve to  $\leq$  Grade 1 within 3 days of the initiation of maximal supportive care
- Grade 3 imAE, excluding colitis or pneumonitis, that does not downgrade to Grade 2 within 3 days after onset of the event despite optimal medical management including systemic corticosteroids or does not downgrade to  $\leq$  Grade 1 or baseline within 14 days
- Grade 3 liver transaminase elevation with concurrent total bilirubin  $> 2 \times$  ULN  Grade  $\geq$  3 non-imAE, except for the exclusions listed below

The following conditions are excluded from the DLT definition:

- Grade 3 fatigue lasting  $\leq$  7 days
- Grade 3 endocrine disorder (thyroid, pituitary, and/or adrenal insufficiency) that is managed with or without systemic corticosteroid therapy and/or hormone replacement therapy and the subject is asymptomatic
- Grade 3 inflammatory reaction attributed to a local antitumor response (eg, inflammatory reaction at sites of metastatic disease, lymph nodes, etc)
- Concurrent vitiligo or alopecia of any AE grade
- Grade 3 infusion-related reaction (first occurrence and in the absence of steroid prophylaxis) that resolves within 6 hours with appropriate clinical management
- Grade 3 or 4 neutropenia that is not associated with fever or systemic infection that improves by at least 1 grade within 3 days.
- Grade 3 or 4 lymphopenia
- Grade 3 thrombocytopenia that is not associated with clinically significant bleeding that requires medical intervention and improves by at least 1 grade within 3 days
- Isolated Grade 3 electrolyte abnormalities that are not associated with clinical signs or symptoms and are reversed with appropriate maximal medical intervention within 3 days
- Transient asymptomatic laboratory abnormalities that do not require hospitalization

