- Permanently discontinue study drug/study regimen for any case meeting Hy's law criteria (AST and/or ALT  $> 3 \times$  ULN + bilirubin  $> 2 \times$  ULN without initial findings of cholestasis (i.e., elevated alkaline P04) and in the absence of any alternative cause.b

until LFT elevations improve or resolve.

If no resolution to Grade  $\leq 1$  in 1 to 2 days, consider discussing with clinical study lead, as needed.

If event is persistent ( $> 2$  to 3 days) or worsens, promptly start prednisone 1 to 2 mg/kg/day PO or IV equivalent.

Grade 3 or 4 For Grade 3

Hold study drug/study

regimen for elevations in transaminases  $\leq 8 \times$  ULN (and no elevations in bilirubin), or elevations in bilirubin  $\leq 5 \times$  ULN until resolution to Grade  $< 1$  or baseline:

- Resume study drug/study regimen if elevations downgrade to Grade  $\leq 1$  or baseline after completion of steroid taper ( $< 10$  mg prednisone or equivalent).
- Permanently discontinue study drug/study regimen for elevations in transaminases  $> 8 \times$  ULN or elevations in bilirubin  $> 5 \times$  ULN.  
For Grade 4 Permanently discontinue study drug/study regimen.

- If still no improvement within 2 to 3 days despite 1 to 2 mg/kg/day methylprednisolone IV or equivalent, promptly start treatment with an immunosuppressants (e.g., mycophenolate mofetil 0.5 – 1 g every 12 hours then taper in consultation with hepatology consult or relevant practice guidelines). Discuss with clinical study lead if mycophenolate is not available. Infliximab should NOT be used.
- Perform Hepatology Consult, abdominal workup, and imaging as appropriate.

---

For Grade 3 or 4

- Promptly initiate empiric IV methylprednisolone at 1 to 2 mg/kg/day or equivalent.

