Grade 3 or 4	Permanently discontinue study drug/study regimen.	For Grade 3 or 4 Carefully monitor serum creatinine daily. Consult nephrologist and consider renal biopsy if clinically indicated. Promptly start prednisone 1 to 2 mg/kg/day PO or IV equivalent. If event is not responsive within 3 to 5 days or worsens despite prednisone at 1 to 2 mg/kg/day PO or IV equivalent, consider additional workup and prompt treatment with an immunosuppressant in consultation with a nephrologist.
Rash or Dermatitis  (Including Pemphigoid)	Any Grade (Refer to NCI CTCAE applicable version in study protocol for definition of severity/grade depending on type of skin rash)	General Guidance  For Any Grade Monitor for signs and symptoms of dermatitis (rash and pruritus). HOLD STUDY DRUG IF STEVENS-JOHNSON SYNDROME (SJS), TOXIC EPIDERMAL NECROLYSIS (TEN), OR OTHER SEVERE CUTANEOUS ADVERSE REACTION (SCAR) IS SUSPECTED. – PERMANENTLY DISCONTINUE STUDY DRUG IF SJS, TEN, OR SCAR IS CONFIRMED.
Grade 1	No dose modifications.	For Grade 1  – Consider symptomatic treatment, including oral antipruritics (e.g., diphenhydramine or hydroxyzine) and topical therapy (e.g., emollient, lotion, or institutional standard).

Grade 2	
For persistent (>1 week) Grade 2 events, hold scheduled study drug/study regimen until resolution to Grade <math>\leq 1</math> or baseline.
 
 
• If toxicity worsens, then treat as Grade 3.
 
• If toxicity improves to Grade <math>\leq 1</math> or baseline, then resume drug/study regimen after completion of steroid taper (< 10 mg prednisone or equivalent).
 
	
For Grade 2
 
 
– Obtain dermatology consult. Consider symptomatic treatment, including oral antipruritics (e.g., diphenhydramine or hydroxyzine) and topical therapy. Consider moderate-strength topical steroid.
 
– If no improvement of rash/skin lesions occurs within 3 days or is worsening despite symptomatic treatment and/or use of moderate strength topical steroid, consider discussing with clinical study lead, as needed, and promptly start systemic steroids such as prednisone 1 to 2 mg/kg/day PO or IV equivalent.
 
– Consider skin biopsy if the event persists for >1 week or recurs.
 

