2, 3, or 4	For Grade 2, 3, or 4 In consultation with relevant pancreatic specialist consider continuing study drug/study regimen if no clinical/radiologic evidence of pancreatitis ± improvement in amylase/lipase.		
 
Consider appropriate diagnostic testing (e.g., abdominal CT with contrast, MRCP if clinical suspicion of pancreatitis and no radiologic evidence on CT) If isolated elevation of enzymes without evidence of pancreatitis, continue immunotherapy.
 

Consider other causes of elevated amylase/lipase

			
 
- If evidence of pancreatitis, manage according to pancreatitis recommendations
 

Acute Pancreatitis	Any Grade (Refer to NCI CTCAE applicable version in study protocol for defining the CTC grade/severity)	General Guidance	
 
- For Any Grade Consider Gastroenterology referral
 

	Grade 2, 3, or 4	For Grade 2 Hold study drug/study regimen dose until resolution to Grade $\leq 1$ . If toxicity improves to Grade $< 1$ or baseline, then resume study drug/study regimen after completion of steroid taper ( $< 10$ mg prednisone, or equivalent).	
 
- For Grade 2, 3, or 4 Promptly start systemic steroids prednisone 1 to 2 mg/kg/day PO or IV equivalent. IV hydration
 

		For Grade 3 or 4 Permanently discontinue study drug/study regimen.	
Neurotoxicity (to include but not limited to non-infectious meningitis, non-infectious encephalitis, and autonomic neuropathy, excluding Myasthenia Gravis and GuillainBarre)	Any Grade (Depending on the type of neurotoxicity, refer to NCI CTCAE applicable version in study protocol for defining the CTC grade/severity)	General Guidance	
 
- For Any Grade Patients should be evaluated to rule out any alternative etiology (e.g., disease progression, infections, metabolic syndromes, or medications). Monitor patient for general symptoms (headache, nausea, vertigo, behavior change, or weakness). Consider appropriate diagnostic testing (e.g., electromyogram and nerve conduction investigations).
 

			
 
- Perform symptomatic treatment with neurological consult as appropriate.
 

- FOR TRANSVERSE  
MYELITIS,  
PERMANENTLY  
DISCONTINUE FOR ANY  
GRADE.

Grade 1	No dose modifications.	For Grade 1

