M  
A  
Y  
2  
0  
2  
2

C

C  
l  
i  
n  
i  
c  
a  
l  
S  
t  
u  
d  
y  
P  
r  
o  
t  
o  
c  
o  
l  
H  
C  
R  
N

V  
considered effective.

r  
s  
i  
o  
n  
D  
a  
t  
e  
:  
0  
9  
M  
A  
Y  
2  
0  
2  
2

C

C  
l  
i  
n  
i  
c  
a  
l  
S  
t  
u  
d  
y  
P  
r  
o  
t  
o  
c  
o  
l  
H  
C  
R  
N

V  
o Patients requiring  
r  
s  
i  
o  
n  
D  
a  
t  
e  
:  
0  
9  
M  
A  
Y  
2  
0  
2  
2

C

C  
l  
i  
n  
i  
c  
a  
l  
S  
t  
u  
d  
y  
P  
r  
o  
t  
o  
c  
o  
l  
H  
C  
R  
N

V

treatment should be started

r  
s  
i  
o  
n  
D  
a  
t  
e  
:  
0  
9  
M  
A  
Y  
2  
0  
2  
2

C

C  
l  
i  
n  
i  
c  
a  
l  
S  
t  
u  
d  
y  
P  
r  
o  
t  
o  
c  
o  
l  
H  
C  
R  
N

V

with IV IG and followed

r  
s  
i  
o  
n  
D  
a  
t  
e  
:  
0  
9  
M  
A  
Y  
2  
0  
2  
2

C

C  
l  
i  
n  
i  
c  
a  
l  
S  
t  
u  
d  
y  
P  
r  
o  
t  
o  
c  
o  
l  
H  
C  
R  
N

V

by plasmapheresis if not

r  
s  
i  
o  
n  
D  
a  
t  
e  
:  
0  
9  
M  
A  
Y  
2  
0  
2  
2

C

C  
l  
i  
n  
i  
c  
a  
l  
S  
t  
u  
d  
y  
P  
r  
o  
t  
o  
c  
o  
l  
H  
C  
R  
N

V  
responsive to IV IG.

r  
s  
i  
o  
n  
D  
a  
t  
e  
:  
0  
9  
M  
A  
Y  
2  
0  
2  
2

C

C  
l  
i  
n  
i  
c  
a  
l  
S  
t  
u  
d  
y  
P  
r  
o  
t  
o  
c  
o  
l  
H  
C  
R  
N

---

V  
e  
r  
s  
i  
o  
n  
D  
a  
t  
e  
:  
0  
9  
M  
A  
Y  
2  
0  
2  
2

C

Myocarditis	Any Grade (Refer to NCI CTCAE applicable version in study protocol for defining the CTC grade/severity)	General Guidance Discontinue drug permanently if biopsyproven immune-mediated myocarditis.	

For Any Grade The prompt diagnosis of immune-mediated myocarditis is important, particularly in patients with baseline cardiopulmonary disease and reduced cardiac function.

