		Grade 2, 3 or 4 	

Consider discussing with the clinical study lead, as needed.

Monitor patients for signs and symptoms of myocarditis (new onset or worsening chest pain, arrhythmia, shortness of breath, peripheral edema). As some symptoms can overlap with lung toxicities, simultaneously evaluate for and rule out pulmonary toxicity as well as other causes (e.g., pulmonary embolism, congestive heart failure, malignant pericardial effusion). Consult a cardiologist early, to promptly assess whether and when to complete a cardiac biopsy, including any other diagnostic procedures.

Initial work-up should include clinical evaluation, BNP, cardiac enzymes, ECG, echocardiogram (ECHO), monitoring of oxygenation via pulse oximetry (resting and exertion), and additional laboratory work-up as indicated. Spiral CT or cardiac MRI can complement ECHO to assess wall motion abnormalities when needed.

Patients should be thoroughly evaluated to rule out any alternative etiology (e.g., disease progression, other medications, or infections)

			
If Grade 2 -- Hold study drug/study regimen dose until resolution to Grade 0. If toxicity rapidly improves to Grade 0, then the decision to reinitiate study drug/study regimen will be based upon treating physician's clinical judgment and after completion of steroid taper. If toxicity does not rapidly improve, permanently discontinue study drug/study regimen.
 
□ If Grade 3-4, permanently discontinue study drug/study regimen.
	
 
- For Grade 2-4           
 
- Monitor symptoms daily, hospitalize. Promptly start IV methylprednisolone 2 to 4 mg/kg/day or equivalent after Cardiology consultation has determined whether and when to complete diagnostic procedures including a cardiac biopsy. Supportive care (e.g., oxygen). If no improvement within 2 to 3 days despite IV methylprednisolone at 2 to 4 mg/kg/day, promptly start immunosuppressive therapy such as TNF inhibitors (e.g., infliximab at 5 mg/kg IV, may be repeated at 2 and 6 weeks after initial dose at the discretion of the treating provider or relevant practice guidelines). Caution: It is important to rule out sepsis and refer to infliximab label for general guidance before using infliximab. Infliximab is contraindicated for patients who have heart failure
 
 
 

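### Section 5.4.1 leaves out a few serious immune toxicities for which Appendix A permanently stops durvalumab, so they do not add to the 3/5 or 4/10 run-in count

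*Combined protocol and SAP*

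**What the plan says.** **What counts as a DLT (Section 5.4.1).** The list includes every Grade 4 immune-mediated event, immune neurotoxicity of any grade, colitis of Grade 3 or higher, Grade 3 non-infectious pneumonitis and slow-resolving Grade 2 pneumonitis. Any other Grade 3 immune event counts if it is a "Grade 3 imAE, excluding colitis or pneumonitis, that does not downgrade to Grade 2 within 3 days after onset of the event", or if it is not back to Grade 1 or baseline within 14 days. The liver item is "Grade 3 liver transaminase elevation with concurrent total bilirubin" above 2 x ULN. Non-immune events of Grade 3 or higher count, subject to listed exclusions. Those exclusions include a first Grade 3 infusion reaction that resolves within 6 hours, and transient laboratory abnormalities without symptoms or hospitalization. No item refers to permanent discontinuation.

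**What ends durvalumab (Appendix A, Specific Immune-Mediated Reactions).**
- Nephritis, Grade 3 or 4: "Permanently discontinue study drug/study regimen".
- Acute pancreatitis: "For Grade 3 or 4 Permanently discontinue study drug/study regimen".
- Myocarditis: "If Grade 3-4, permanently discontinue study drug/study regimen". In addition, "Discontinue drug permanently if biopsyproven immune-mediated myocarditis", under the any-grade guidance. Grade 2 myocarditis that does not rapidly improve is also a permanent stop.
- Hepatitis, within the Grade 2 guidance: "Permanently discontinue study drug/study regimen for any case meeting Hy's law criteria".
- Intestinal perforation: permanent stop at any grade.

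**How the count is used (Sections 5.4 and 12.7).** Enrollment halts for re-evaluation at 3 DLTs in the first 5 patients or 4 in the first 10. Run-in subjects who do not stay on study through the DLT period for a non-DLT reason are replaced.

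**The concern.** Sections 6.1.1 and 6.1.3 allow no durvalumab dose reduction, so permanent discontinuation is the strongest dose limitation this regimen has. For a few serious organ toxicities, an event can end durvalumab and still not be dose-limiting for the halt rule. Safety and feasibility form a primary objective (Section 2.1.1). A patient stopped before consolidation also cannot be evaluable for 12-month PFS, because Section 12.5 requires at least one consolidation dose.

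What is at stake is a run-in whose count is one short of the boundary. There, one uncounted myocarditis or Hy's law case decides whether accrual formally halts or continues.

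**Working it through.** **1. Set the two lists side by side.**

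| Event ending durvalumab under Appendix A | Status in 5.4.1 |
|---|---|
| Hy's law case with Grade 2 transaminases | Not counted, unless the bilirubin rise itself meets a DLT item (the liver item needs Grade 3 transaminases) |
| Grade 2 myocarditis, biopsy-proven or not rapidly improving | Not counted; no item covers it |
| Intestinal perforation below the DLT grades | Not counted |
| Grade 3 immune myocarditis, nephritis or acute pancreatitis | Not counted if at Grade 2 within 3 days and at Grade 1 or baseline within 14 days; otherwise a DLT |

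**2. Follow the patient through the count.** Section 5.4 replaces subjects who do not remain on study for a non-DLT reason. Section 6.2 says patients taken off protocol therapy are still followed, and Section 6.3 separates leaving therapy from leaving the protocol. On that reading the patient stays in the 5 or 10 as a non-DLT. But the DLT period is defined by completing two consolidation cycles, which a permanently stopped patient may never do, so a site could replace the patient. The text does not settle this. Neither reading adds to the count.

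**3. Reproduce the plan's boundaries.** Inputs from Section 12.7: DLT rates 10% versus 30%, type I error 0.05, power 0.8. The Wald upper limit is ln(0.8/0.05) = 2.773. Each DLT adds ln(0.3/0.1) = 1.099 and each non-DLT adds ln(0.7/0.9) = −0.251. The number of DLTs needed is (2.773 + 0.2513n)/(1.0986 + 0.2513).
- n = 5: 2.98, so 3.
- n = 10: 3.92, so 4.

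Both match the plan. They depend only on the rates and error levels, so adding events to the definition does not move them.

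**4. Halt probability of the two-look rule.** With X the DLTs in the first 5 and Y those in the second 5:

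P(halt) = P(X ≥ 3) + Σ (x = 0 to 2) P(X = x) · P(Y ≥ 4 − x).

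At 20%: 0.05792 + 0.00220 + 0.02372 + 0.05381 = 0.1377.

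The documents give no frequency for the uncounted events. The nearest figure, in Section 1.3.1.1, is about 4% permanent discontinuation for any adverse event on durvalumab monotherapy, which is far broader. I assume 0.25 to 2 added points, net of patients who already have a counted DLT.

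| Counted DLT rate | As written | +0.25 points | +1 point | +2 points |
|---|---|---|---|---|
| 10% | 1.8% | 1.9% | 2.4% | 3.1% |
| 20% | 13.8% | 14.2% | 15.7% | 17.7% |
| 30% | 37.3% | 37.9% | 39.9% | 42.6% |

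The "as written" column keeps the patient as a non-DLT. If the patient is replaced, the counted rate at 20% becomes 0.20/(1 − 0.0025) = 20.05% to 0.20/(1 − 0.02) = 20.4%. The starting halt probability is then 13.9% to 14.5%, so the fix adds less.

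**5. Effect when exactly one such patient occurs.** The other nine have DLT rate p, and the patient's position is averaged over the first and second five. Counting that patient turns a continue into a halt in 5.5%, 18.7% and 26.7% of run-ins at p = 10%, 20% and 30%. If the current text would replace the patient, multiply by (1 − p): 5.0%, 14.9% and 18.7%. These figures are conditional. At a 1% event rate the chance of at least one such patient in 10 is 1 − 0.99^10 = 9.6%.

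**The case against.** The strongest reply is that 5.4.1 deliberately judges most Grade 3 immune events by reversibility. Appendix A calls itself a recommendation and also covers other durvalumab and tremelimumab settings. Nothing says the two lists must agree, and for colitis 5.4.1 is the stricter: Grade 3 is a DLT, while Appendix A lets a PD-L1 inhibitor resume after recovery. This stands as an argument against aligning the lists in full. It does not explain why a Hy's law case, or Grade 2 myocarditis that fails to improve, should carry no weight, since neither is excluded for reversing quickly.

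The gap is also narrow. Grade 3 renal or pancreatic events attributed to chemoradiation rather than to durvalumab fall under the non-immune item, which has no general recovery condition. That stands and is why the size is small.

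Finally, the events are seen. Section 6 has discontinuation events evaluated. Section 11.1.8 makes potential Hy's law cases SAEs unless an unrelated cause is confirmed, and interrupts dosing when no definitive diagnosis is found. The DSMB reviews adverse event summaries around both run-in looks and may call extra meetings (Section 13.1). It can therefore act by judgement, but its judgement does not change the count.

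A reader might infer that every Appendix A permanent stop should be a DLT, including the hepatitis line "Permanently discontinue study drug/study regimen for elevations in transaminases" above 8 x ULN or bilirubin above 5 x ULN. The documents do not support that. The exclusion for transient laboratory abnormalities looks deliberate for isolated enzyme or bilirubin rises, as does the one for brief infusion reactions.

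**Conclusion.** The point holds as a narrow gap in the DLT definition. The four groups of events in step 1 can end durvalumab without adding to 3/5 or 4/10, whether the patient is kept or replaced.

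The average effect is small: about 0.5 to 4 percentage points of halt probability at a 20% DLT rate, before allowing for replacement. This rests on an assumed 0.25 to 2 added points that the documents neither support nor rule out. The upper end would be half of the 4% monotherapy figure for all adverse events. That figure is not a strict cap in a chemoradiation setting, but it suggests that 2 points is generous.

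Two inferences should be avoided. These toxicities are not unmonitored. Nor is it established that such a patient always stays in the denominator. This is a cheap improvement of low priority, not an error that undermines the run-in.

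**What to change.** Add to 5.4.1:

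> The following durvalumab-related events in the DLT period are DLTs regardless of recovery: a Hy's law case (AST/ALT >3 x ULN with bilirubin >2 x ULN, no alternative cause); biopsy-proven myocarditis; or myocarditis, intestinal perforation, nephritis or acute pancreatitis for which durvalumab is permanently discontinued under Appendix A. Such patients are not replaced.

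State that the transient-laboratory exclusion does not apply to Hy's law cases. Keep that exclusion for isolated enzyme or bilirubin rises, and leave the infusion-reaction exclusion unchanged. Add a line to the DSMB report at both run-in looks giving the number of toxicity-related permanent durvalumab discontinuations.

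The cost is a short addition to 5.4.1 and one report line, with no change to patient care or to the boundaries. The downside is a slightly broader DLT definition than the one behind the 10% versus 30% rates, and so a slightly higher chance of a halt. Even with 2 points added to a 10% rate, that chance is 3.1%, below the nominal 0.05. Section 5.4 also makes a halt a re-evaluation of accrual rather than automatic termination.

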## 5.5 Concomitant Medications

All concomitant medications received within 28 days before the first dose of trial treatment and 30 days after the last dose of trial treatment should be recorded. Concomitant medications administered more than 30 days after the last dose of trial treatment should be recorded for serious adverse events (SAE).

### 5.5.1 Allowed Concomitant Medications

All treatments that the investigator considers necessary for a subject's welfare may be administered at the discretion of the investigator in keeping with the community standards of medical care. All concomitant medication will be recorded on the case report form (CRF) including all prescription, over-the-counter (OTC), and IV medications and fluids. If changes occur during the trial period, documentation of drug dosage, frequency, route, and date may also be included on the CRF.

### 5.5.2 Prohibited Concomitant Medications

Medications or vaccinations specifically prohibited in the exclusion criteria are not allowed during the ongoing trial. If there is a clinical indication for one of these or other medications or vaccinations specifically prohibited during the trial, discontinuation from trial therapy or vaccination may be required. The site investigator should discuss any questions regarding this with HCRN who will then communicate with the sponsor-investigator and AstraZeneca regarding the situation. The final decision on any supportive therapy or vaccination rests with the site investigator and/or the subject's primary physician. There are no prohibited therapies during the Post-Treatment Follow-up Phase.

Subjects are prohibited from receiving the following therapies during the Screening and Treatment Phase of this trial:

- Antineoplastic systemic chemotherapy or biological therapy not specified in this protocol
- Immunotherapy not specified in this protocol
- Chemotherapy not specified in this protocol
- Investigational agents other than Durvalumab
- Live vaccines within 30 days prior to the first dose of trial treatment and while participating in the trial. Examples of live vaccines include, but are not limited to, the following: measles, mumps, rubella, varicella/zoster, chicken pox, yellow fever, rabies, BCG, and typhoid (oral) vaccine. Seasonal influenza vaccines for injection are generally killed virus vaccines and are allowed; however intranasal influenza vaccines (e.g. FluMist®) are live attenuated vaccines, and are not allowed.
- Systemic glucocorticoids (>10 mg prednisone equivalent) for any purpose other than to modulate symptoms from an event of clinical interest of suspected immunologic etiology. Brief, limited use of systemic corticosteroids ( $\leq 7$  days) are permitted where such use is considered standard of care (e.g. as premedication for contrast allergy or for COPD exacerbation). Inhaled or topical steroids, and adrenal replacement doses of steroids (for example prednisone 10mg daily) are permitted while on study.
- Would advise patients avoid herbal or natural remedies with reported immunemodulating effects.
- Hematopoietic growth factor support will not be allowed during chemoradiation.

Subjects who, in the assessment by the site investigator, require the use of any of the aforementioned treatments for clinical management should be removed from the trial.

There are no prohibited therapies during the Post-Treatment Follow-up Phase.

